11. SAFETY ANALYSES

The safety analysis will be performed using the safety analysis set. Safety variables include AEs, clinical laboratory variables, vital signs, and ECG variables, antibody testing, and neurologic assessments. For each safety variable, the last available value on or before first study dosing date (Day 1) is defined as the baseline. A Final on-Treatment Assessment (FoTA) will be defined as the last observation recorded within the period in which the treatment is administered.

11.1. Adverse Events

Adverse events will be coded using Version 19.1 or newer of MedDRA.

An AE is any untoward medical occurrence in a clinical investigation subject administered a product or medical device; the event need not necessarily have a causal relationship with the treatment or usage.

An AE (classified by preferred term) that occurs during the study will be considered a treatment-emergent AE (TEAE) if it has a start date and time on or after the first dose of investigational product or if it has a start date and time before the date and time of the first dose of investigational product, but increases in severity on or after the date and time of the first dose of investigational product. If more than 1 AE with the same preferred term is reported before the date and time of the first dose of investigational product, then the AE with the greatest severity will be used as the benchmark for comparison to the AEs occurring after dose of investigational product under the preferred term. For the purposes of summarizing by treatment period, an AE will be considered to be treatment emergent in Treatment Period 1 if it has a start date or increases in severity during open label Treatment Period 1; an AE will be considered to be treatment emergent in Treatment Period 2 if it has a start date or increases in severity during open label Treatment Period 2; an AE will be considered to be treatment emergent in the Follow-up Period if it has a start date or increases in severity during the Follow-up Period.

An overall summary of the number of subjects with TEAEs will be presented by treatment group, overall and for each of the periods that includes the number and percentage of subjects with:

- Any TEAEs,
- Any serious TEAEs,
- Any TEAEs related to investigational product,
- Any serious TEAEs related to investigational product,
- Any TEAEs leading to discontinuation of investigational product,
- Any severe TEAEs,
- Any TEAE leading to death

The number and percentage of subjects reporting TEAEs in each treatment group, overall and for each of the periods, will be tabulated in the following ways:

- By system organ class (SOC) and preferred term (PT),
- Common TEAEs ($\geq 5\%$ of subjects in all doses group) by PT
- By SOC, PT, and maximum severity,
- TEAEs considered related to investigational product by SOC and PT.
- Serious TEAEs by SOC and PT,
- TEAEs leading to withdrawal of investigational product by SOC and PT

If more than 1 AE occurs with the same preferred term for the same subject, then the subject will be counted only once for that preferred term using the most severe and most related occurrence for the summarization by severity and by relationship to investigational product.

All information about AEs collected on the eCRF will be listed alongside the treatment, preferred term, and SOC. For injection site AEs, serious AEs, deaths, AEs related to investigational product, and TEAEs leading to study discontinuation, a separate listing will also be provided.

An additional summary of AE's and SAE's by SOC and PT occurring after initiation of additional biologic therapy will be performed by additional biologic (anti-TNF (Infliximab, Adalimumab, Certolizumab, Certolizumab Pegol, Golimumab) vs. Vedolizumab vs. Other Biologics (Ustekinumab)) received in the follow-up period. For this analysis subjects who have adverse events after the first dose of additional biologic therapy will be considered treatment emergent.

Furthermore the following listings will be provided: listing of TEAEs of Myalgia, listing of Clostridium difficile infection adverse events, listing of Gastroenteritis adverse events, listing of injection site reactions and listing of Nasopharyngitis adverse events.

11.2. Clinical Laboratory Variables

Descriptive statistics for clinical laboratory values (in SI units) and changes from baseline at each assessment time point as well as shift tables from baseline to each visit for quantitative variables will be presented by treatment group for the following clinical laboratory variables:

Hematology Hemoglobin, hematocrit, red blood cell (RBC) count, white blood cell (WBC) count, platelet count, total neutrophils (Abs), eosinophils(Abs), monocytes (Abs), basophils (Abs), lymphocytes (Abs)

Biochemistry Blood urea nitrogen (BUN), creatinine, glucose, sodium, potassium, chloride, aspartate aminotransferase (AST), alanine aminotransferase (ALT), alkaline phosphatase (ALP), creatine phosphokinase (CPK and CPK fractionation), bilirubin (total and direct), calcium, total protein, albumin, uric acid, NT-proBNP and Troponin I.

Urinalysis Dipstick (pH, protein, glucose, ketones, blood, leukocyte esterase, and nitrites). **NOTE:** microscopic evaluation (RBCs, WBCs, crystals, casts, and bacteria) will be performed when indicated by the dipstick results.

Other JC virus DNA testing, JC virus Serology (antibody).

Clinical laboratory test values are potentially clinically important (PCI) if they meet either the low or high PCI criteria listed in Table 5: Criteria for Potentially Clinically Important Laboratory Tests. The number and percentage of subjects with post-baseline PCI values will be tabulated by treatment group, overall and by Open Label Treatment Period. The percentages will be calculated relative to the number of subjects with available baseline values and at least 1 post-baseline assessment. The numerator is the total number of subjects with at least 1 post-baseline PCI value. A supportive listing of subjects with post-baseline PCI values will be provided including the subject number, site, baseline, and post-baseline values.

Parameter	Age Range	Gender	Outlier Criteria ¹	
			Low	High
Hematology				
Eosinophils (%)	All	Male, Female	NA	>0.6x10 ³ /uL
Hemoglobin	All	Male, Female	<9g/dL	NA
Neutrophils (%)	All	Male, Female	<1.5x10 ³ /uL	>8.0x10 ³ /uL
Platelets	All	Male, Female	<75.0x10 ³ /uL	>500.0x10 ³ /uL
Leukocytes (WBC)	All	Male, Female	<3.0x10 ³ /uL	>16.0x10 ³ /uL
Lymphocytes	All	Male, Female	<0.8xLLN	>1.2xULN
Monocytes	All	Male, Female	<0.1x10 ³ /uL	>1.1x10 ³ /uL
Chemistry				
Albumin	All	Male, Female	<3g/dL	NA
Alkaline Phosphatase	All	Male, Female	NA	>2.5 x ULN
Alanine Aminotransferase (ALT)	All	Male, Female	NA	>2.5 x ULN
Aspartate Aminotransferase (AST)	All	Male, Female	NA	>2.5 x ULN
DILI Screen (ongoing safety monitoring)	All	Male, Female		AST or ALT >3 x ULN and TBL >2 x ULN

Table 5: Criteria for Potentially Clinically Important Laboratory Tests				
Parameter	Age Range	Gender	Outlier Criteria ¹	
			Low	High
Total Bilirubin	All	Male, Female	NA	>1.5 x ULN
Direct Bilirubin	All	Male, Female	NA	>1.5 x ULN
Blood Urea Nitrogen (BUN)	All	Male, Female	NA	>2.5 x ULN
Calcium	All	Male, Female	< 8mg/dL	>11.5mg/dL
Chloride	All	Male, Female	< 90mEq/L	>115mEq/L
Creatinine	All	Male, Female	NA	>1.5 x ULN
Potassium	All	Male, Female	< 3.5mEq/L	>5.5mEq/L
Total Protein	All	Male, Female	< 5g/dL	>9g/dL
Glucose	All	Male, Female	< 55mg/dL	>160mg/dL
Sodium	All	Male, Female	< 130mEq/L	>150mEq/L
NT-proBNP	All	Male, Female		>300 pg/mL
Troponin I	All	Male, Female		>0.03ug/L
CK-MB	All	Male, Female		≥25 U/L
Uric acid, Serum	All	Males		>10mg/dL
Uric acid, Serum	All	Females		>9mg/dL
Creatinine phosphokinase (CPK)	All	Male, Female		>2.5 x ULN
Urinalysis				
Leukocyte esterase	All	Male, Female	Present	Present
Protein	All	Male, Female	NA	> 2+
Glucose	All	Male, Female	NA	>1+
Blood	All	Male, Female	NA	>2+

NA=Not Applicable; LLN=Lower Limit of Normal; ULN=Upper Limit of Normal; Intl.=International.

¹ If criteria in both directions are shown for a single parameter, then abnormalities in each direction are summarized separately.

A separate listing of CPK data, of subjects with AE of Myalgia, defined as subjects with preferred term of Myalgia, will be presented.

Hy's law

Abnormal values in aspartate transaminase (AST) and/or alanine transaminase (ALT) concurrent with abnormal elevations in total bilirubin that meet the criteria outlined below in the absence of other causes of liver injury are considered potential cases of drug-induced liver injury (potential Hy's Law cases).

The threshold of laboratory abnormalities for a potential case of drug-induced liver injury depends on the subject's individual baseline values and underlying conditions:

- Subjects with AST or ALT and total bilirubin baseline values within the normal range who subsequently present with AST or ALT ≥ 3 times the upper limit of normal (X ULN) concurrent with a total bilirubin ≥ 2 X ULN with no evidence of hemolysis and an alkaline phosphatase ≤ 2 X ULN or not available.
- For subjects with preexisting ALT or AST or total bilirubin values above the upper limit of normal, the following threshold values should be used in the definition mentioned above:
 - For subjects with pre-existing AST or ALT baseline values above the normal range: AST or ALT ≥ 2 times the baseline values and ≥ 3 X ULN, or ≥ 8 X ULN (whichever is smaller).

Concurrent with

- For subjects with pre-existing values of total bilirubin above the normal range: Total bilirubin increased by one time the upper limit of normal or ≥ 3 times the upper limit of normal (whichever is smaller).

Subjects potentially meeting Hy's law will be listed.

JC Virus

JC virus antibody will be summarized at baseline of 1009 by treatment group. A shift table from baseline of 1009 to the end of study at each visit will be presented by treatment group in study A7281010.

Any subjects that have a seroconversion (change from negative to positive) or a seroconversion from the baseline of 1009 at any point in either the 1009 or 1010 study will be listed.

JC virus antibody will be listed. JC virus DNA will not be analyzed.

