11.3. Vital Signs

Descriptive statistics for vital signs (e.g., systolic and diastolic blood pressure, pulse rate, temperature and body weight) and their changes from baseline at each post-baseline visit and at the end of study will be presented by treatment group.

Vital sign values will be considered PCI if they meet both the observed value criteria and the change from baseline criteria listed in Table 6: Criteria for Potentially Clinically Significant Vital Signs. The number and percentage of subjects with PCI post-baseline values will be tabulated by treatment group and overall,. The percentages will be calculated relative to the number of subjects with baseline and at least 1 post-baseline assessment. The numerator is the total number of subjects with at least 1 PCI post-baseline vital sign value. A supportive listing of subjects with post-baseline PCI values will be provided including the subject number, baseline, and post-baseline PCI values.

Table 6: Criteria for Potentially Clinically Significant Vital Signs			
Vital Sign Parameter	Flag	Criteria^a	
		Observed Value	Change from Baseline
Systolic blood pressure (mmHg)	High	≥180	Increase of ≥20
	Low	≤90	Decrease of ≥20
Diastolic blood pressure (mmHg)	High	≥105	Increase of ≥15
	Low	≤50	Decrease of ≥15
Pulse rate (beats per minute)	High	≥120	Increase of ≥15
	Low	≤50	Decrease of ≥15
Weight (kg)	High	-	Increase of ≥10%
	Low	-	Decrease of ≥10%
BMI (kg/m ²)	High	-	Increase of ≥10%
	Low	<18	Decrease of ≥10%

^a A post-baseline value is considered as a PCI value if it meets both criteria for observed value and change from baseline.

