11.4. Electrocardiogram (ECG) and Echocardiogram (ECHO)

Descriptive statistics for ECG variables (e.g., heart rate, PR interval, RR interval, QRS interval, QT interval, and QTc interval (QTcB and QTcF) and their changes from baseline at each assessment time point will be presented by treatment group. ECG interpretation will be summarized by visit. A shift table from baseline to each visit for qualitative ECG results will be presented.

Electrocardiogram variable values will be considered PCI if they meet or exceed the upper limit values listed in Table 7: Criteria for Potentially Clinically Important ECG Values. The number and percentage of subjects with post-baseline PCI values will be tabulated by treatment group and overall. The percentages will be calculated relative to the number of subjects with available baseline and at least 1 post-baseline assessment. The numerator is the total number of subjects with at least 1 PCI post-baseline ECG value. A listing of all subjects with post-baseline PCI value will be provided including the subject number, site, baseline, and post-baseline PCI values.

Echocardiogram data will be listed.

Table 7: Criteria for Potentially Clinically Important ECG Values		
ECG Parameter	Unit	Higher Limit
QRS Interval	msec	≥150
PR Interval	msec	≥250
QTcB Interval	msec	≥500
QTcF Interval	msec	≥500

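### Laboratory and ECG PCI percentages mix new abnormalities with those already present at the A7281010 baseline, and no planned table gives the rate of new ones

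*SAP*

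**What the plan says.** **Laboratory (SAP 11.2).** The criterion is a fixed limit: "Clinical laboratory test values are potentially clinically important (PCI) if they meet either the low or high PCI criteria listed in Table 5". The denominator is "The percentages will be calculated relative to the number of subjects with available baseline values and at least 1 post-baseline assessment". The numerator is "The numerator is the total number of subjects with at least 1 post-baseline PCI value". On layout: "The number and percentage of subjects with post-baseline PCI values will be tabulated by treatment group, overall and by Open Label Treatment Period".

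**ECG (SAP 11.4).** The construction is the same: "Electrocardiogram variable values will be considered PCI if they meet or exceed the upper limit values listed in Table 7", "The percentages will be calculated relative to the number of subjects with available baseline and at least 1 post-baseline assessment" and "The numerator is the total number of subjects with at least 1 PCI post-baseline ECG value".

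**Vital signs (SAP 11.3, Table 6 footnote).** Here the baseline value enters the definition: "A post-baseline value is considered as a PCI value if it meets both criteria for observed value and change from baseline".

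**Related rules.** Section 11 takes baseline as the most recent value up to the first A7281010 dose. Section 17.3 lets every post-baseline assessment, including repeats and unscheduled ones, count towards PCI. It adds no rule for subjects who were PCI at baseline.

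**The concern.** The laboratory and ECG rules require a baseline value but do not use it to decide who is counted. A subject whose platelets, albumin or NT-proBNP were past the limit before the first extension dose, and are past it once more afterwards, counts the same as a subject who crossed the limit for the first time.

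Such baselines are foreseeable. The cardiac-monitoring footnotes in section 2.4 provide for an NT-proBNP above 300 pg/mL at baseline, which is exactly the Table 5 limit. Subjects had moderate to severe colitis and enter whether or not they responded in A7281009 (section 2.1).

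Safety and tolerability are the primary objective (section 3.1). A reader of the PCI tables will want to know how many subjects became abnormal during the extension, and those tables cannot say. The laboratory tables by treatment period can also show the same long-standing abnormality in both periods. Two of the section 5 columns, 75 mg without escalation and 75 to 225 mg, are defined by what happened after randomization, and section 10.3.2 links escalation to loss of response. Randomization does not balance baseline abnormalities between those two columns.

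**Working it through.** The SAP states no PCI rate, so there is no figure to reproduce. The check has two parts.

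**1. Does any other planned output give the rate of new PCI values?**

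- Laboratory shift tables (11.2; Tables 14.3.4.5 to 14.3.4.7) run from baseline to each visit. They are per visit, not per subject over a period, and the SAP does not say that their categories are the Table 5 limits.
- The ECG shift table (11.4; Table 14.3.6.6) covers the qualitative result only, not the Table 7 interval limits.
- The PCI listings in both sections show baseline beside later values. A reader can trace each subject, but would have to build the rate by hand.
- The Hy's law thresholds (11.2) do depend on baseline, but they cover only liver tests.

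So none of these outputs gives a subject-level rate of new PCI values.

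**2. How much could the mixing matter?**

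All three inputs are assumptions:

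- b = proportion of subjects PCI at baseline
- q = proportion of those with at least one later PCI value
- i = proportion newly PCI among subjects not PCI at baseline

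Reported proportion under the written rule = b·q + (1 − b)·i

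Share of counted subjects already PCI at baseline = b·q / [b·q + (1 − b)·i]

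With i = 5% and q = 60%:

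| b | b·q | (1 − b)·i | Reported | Already PCI at baseline |
|---|---|---|---|---|
| 0% | 0 | 5.00% | 5.00% | 0% |
| 5% | 3.00% | 4.75% | 7.75% | 3.00/7.75 = 39% |
| 10% | 6.00% | 4.50% | 10.50% | 6.00/10.50 = 57% |
| 15% | 9.00% | 4.25% | 13.25% | 9.00/13.25 = 68% |

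In subjects, using the expected enrolment of about 270 (section 2.5) and b = 10%: 27 are PCI at baseline, of whom 0.6 × 27 = 16.2 are counted. Of the other 243, 0.05 × 243 = 12.15 are counted. The total is 28.35/270 = 10.5%. The rate among subjects not PCI at baseline is 12.15/243 = 5%.

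The reported figure is twice the new rate when 0.6b + 0.05(1 − b) = 0.10, that is 0.55b = 0.05, so b ≈ 9%.

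Over wider ranges (b 2% to 15%, q 50% to 100%, i 2% to 10%), the share of counted subjects already PCI at baseline runs from 9% to 90%. The answer therefore depends almost wholly on rates that the SAP does not contain.

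For group comparisons, the table also shows that two groups with the same 5% new rate but baseline prevalence of 5% and 10% would be reported as 7.75% and 10.5%. That difference comes from baseline alone.

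**A wording gap.** The numerator is not restricted to members of the denominator. Read literally, a subject with no baseline value could be counted above the line but not below it.

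**The case against.** The strongest defence is that the rule is explicit, can be programmed, and is honestly labelled. The SAP calls these values post-baseline and never treatment-emergent. A reader might infer from the by-period laboratory tables that the counts are new on-treatment findings, but the text does not claim that. This stands: the SAP contains no false statement here, only a summary that cannot answer an obvious question.

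The second defence concerns the design. A7281010 baseline is the Week 12 or final visit of A7281009 (section 2.4), after a 12-week induction in which some subjects received SHP647. A reader might infer that a PCI value at this baseline is existing colitis and should be removed. The documents do not support that, because the abnormality may have arisen on the drug. Making exclusion the lead definition could under-report drug effects. It would also lose worsening, for example an NT-proBNP just above 300 pg/mL at baseline that later rises several-fold. This stands too, and it shapes the fix.

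Third, the vital-sign rule is not a model for exclusion. Table 6 asks for a change but does not bar subjects already past the limit: a systolic pressure of 182 rising to 205 mmHg meets both parts. It shows that the SAP uses baseline in one domain, not that the other two contradict it.

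Fourth, the size is assumed, and the Table 7 limits (such as QTc of 500 msec or more) are far out. Starting dose is randomized 1:1 and no hypothesis is tested, so imbalance between the 75 mg overall and 225 mg groups would be due to chance. This limits the concern about dose comparison to chance imbalance and to the columns split by escalation.

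**Conclusion.** The concern holds in a limited form. Under sections 11.2 and 11.4, abnormalities present at the A7281010 baseline enter the laboratory PCI percentages and, probably to a small extent, the ECG ones. No planned table separates them from new ones at subject level.

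The size cannot be known from the SAP. On the assumed 5% new rate and 60% persistence, the reported figure would be 7.75% to 13.25% for baseline prevalence of 5% to 15%. With no baseline abnormality the present count and the new rate coincide. A reader might conclude that the tables will at least double the true rate. On these inputs that requires a baseline prevalence of about 9% or more, and nothing in the document shows that any parameter reaches it.

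This is a cheap improvement to the tables that serve the primary objective, not an error that invalidates them.

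**What to change.** In sections 11.2 and 11.4, and in the PCI table shells:

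1. Keep the present post-baseline PCI count as the lead row, and state that the numerator is drawn only from subjects in the denominator.
2. Add row (a): subjects who did not meet the same criterion (same parameter and direction) at baseline, with that group as the denominator.
3. Add row (b): subjects who met it at baseline, shown with their change from baseline so that worsening stays visible.
4. Show row (b) by A7281009 treatment, placebo versus SHP647, a split the SAP already uses for efficacy in section 10.2. Do not describe row (b) as disease that pre-dates SHP647.

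This uses data already collected. The cost is a little more programming, longer tables, and denominators that differ from one parameter to the next and so must be printed with each percentage.

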11.3. Vital Signs

Descriptive statistics for vital signs (e.g., systolic and diastolic blood pressure, pulse rate, temperature and body weight) and their changes from baseline at each post-baseline visit and at the end of study will be presented by treatment group.

Vital sign values will be considered PCI if they meet both the observed value criteria and the change from baseline criteria listed in Table 6: Criteria for Potentially Clinically Significant Vital Signs. The number and percentage of subjects with PCI post-baseline values will be tabulated by treatment group and overall,. The percentages will be calculated relative to the number of subjects with baseline and at least 1 post-baseline assessment. The numerator is the total number of subjects with at least 1 PCI post-baseline vital sign value. A supportive listing of subjects with post-baseline PCI values will be provided including the subject number, baseline, and post-baseline PCI values.

Table 6: Criteria for Potentially Clinically Significant Vital Signs			
Vital Sign Parameter	Flag	Criteria^a	
		Observed Value	Change from Baseline
Systolic blood pressure (mmHg)	High	≥180	Increase of ≥20
	Low	≤90	Decrease of ≥20
Diastolic blood pressure (mmHg)	High	≥105	Increase of ≥15
	Low	≤50	Decrease of ≥15
Pulse rate (beats per minute)	High	≥120	Increase of ≥15
	Low	≤50	Decrease of ≥15
Weight (kg)	High	-	Increase of ≥10%
	Low	-	Decrease of ≥10%
BMI (kg/m ²)	High	-	Increase of ≥10%
	Low	<18	Decrease of ≥10%

^a A post-baseline value is considered as a PCI value if it meets both criteria for observed value and change from baseline.

11.4. Electrocardiogram (ECG) and Echocardiogram (ECHO)

Descriptive statistics for ECG variables (e.g., heart rate, PR interval, RR interval, QRS interval, QT interval, and QTc interval (QTcB and QTcF) and their changes from baseline at each assessment time point will be presented by treatment group. ECG interpretation will be summarized by visit. A shift table from baseline to each visit for qualitative ECG results will be presented.

Electrocardiogram variable values will be considered PCI if they meet or exceed the upper limit values listed in Table 7: Criteria for Potentially Clinically Important ECG Values. The number and percentage of subjects with post-baseline PCI values will be tabulated by treatment group and overall. The percentages will be calculated relative to the number of subjects with available baseline and at least 1 post-baseline assessment. The numerator is the total number of subjects with at least 1 PCI post-baseline ECG value. A listing of all subjects with post-baseline PCI value will be provided including the subject number, site, baseline, and post-baseline PCI values.

Echocardiogram data will be listed.

Table 7: Criteria for Potentially Clinically Important ECG Values		
ECG Parameter	Unit	Higher Limit
QRS Interval	msec	≥150
PR Interval	msec	≥250
QTcB Interval	msec	≥500
QTcF Interval	msec	≥500

